Rationale	
Our primary hypothesis is that up to ten sequential 24-hour SCD treatments will improve survival in pediatric patients with Acute Kidney Injury (AKI) as compared to CRRT alone (standard of care). Further, SCD therapy will reduce the duration of maintenance dialysis secondary to AKI due to acute tubular necrosis (ATN). ATN is an acute reversible process and if not reversed in three months, it may not be reversed at all. [1, 2] Studies suggest that approximately 10-20% of AKI patients do not recover renal function [3, 4] and, therefore, require chronic dialysis.
 
Importantly, acute kidney injury is a highly lethal condition in critically ill patients. Despite improvements in acute medical care and advances in dialysis therapies, the mortality rate during the past four decades of this condition has not improved. Critically ill patients with AKI in hospital ICU settings have mortality rates of approximately 50%, including pediatric patients [5, 6, 7, 8, 9, 10, 11, 12]
 
AKI promotes a systemic inflammatory response syndrome (SIRS) which results in systemic microvascular damage and, if severe, multi-organ dysfunction. [13, 14] Activated circulating

	leukocytes play a central role in this process. [15] Leukocytes, especially neutrophils, are major contributors to the pathogenesis and progression of many inflammatory disorders, including SIRS, sepsis, ischemia reperfusion injury, and acute respiratory distress syndrome (ARDS). Many therapeutic approaches are under investigation to limit the activation and tissue accumulation of leukocytes at sites of inflammation to minimize tissue destruction and disease progression. [16, 17, 18]
Primary Objective	To evaluate the safety of up to ten consecutive 24 hour SCD treatments in the pediatric AKI population being treated with Continuous Renal Replacement Therapy (CVVH, CVVHD, or CVVHDF) with regional citrate anticoagulation.
Secondary Objective	To assess the effect of SCD treatment on various measures of pediatric patient clinical outcomes and to evaluate the integrity of the SCD device and patient safety in SCD treatments from the time of initiation of therapy to as many as ten consecutive 24-hour SCD treatments.

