Study Endpoints	
In this Pilot study four domains of interest have been designated. The four domains are:
 
 • Patient Safety: Safety Endpoint Measures include adverse events, laboratory safety parameters, vital signs, EKG, ventilation status and hemodynamic variables. • Clinical Efficacy: The Primary Clinical Efficacy Endpoint Measure is in-hospital; 28 and 60-day all-cause mortality. Time to renal recovery and necessity for chronic dialysis up to day 60 will also be determined. Additional efficacy endpoints include time to intensive care unit (ICU) discharge, and time to hospital discharge. • Device Integrity and Performance: The Endpoint Measure is SCD use without failure. This measure will help assess the integrity and performance of the SCD device. • SCD Mode of Action: Exploratory Endpoint Measures will include inflammatory cytokines, cell activation parameters and biomarkers at clinical sites with this capability. The analysis will be performed at a central laboratory.
Assessment of Device Integrity and Performance	
Criteria for assessment of device integrity and performance include:
 
 • Significant Clotting within the Device as assessed by visual inspection. • Evidence of leakage (i.e., cracking/breakage of a port, connector, hemofilter cartridge or tubing).

	
 Any unforeseen malfunction that results in the need for discontinuation.
Study Populations	Pediatric patients with a body weight (BW) between ≥ 10 and ≤ 20 kg receiving care in the Intensive Care Units of each participating hospital will be screened daily and identified for participation in the trial.
Study Design	This is an open-label, multi-center Pilot study.
Approximate Number of Subjects	Up to 10 patients will be enrolled in this study.
Approximate Number of Centers	Up to 7 Clinical Centers in the United States will participate in this study.
Duration of Subject Participation	Each patient will be followed for 60 days following enrollment.

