	
 4. Presence of preexisting advanced chronic renal failure (i.e., ESRD) requiring chronic renal replacement therapy prior to this episode of acute kidney injury or with pre-existing chronic kidney disease (CKD) defined as an eGFR<30 ml/min/1.73m². Patients who have never seen a pediatric nephrologist will be assumed not to have pre-existing CKD. 5. AKI occurring in the setting of burns, obstructive uropathy, scleroderma renal crisis, atheroembolism, functional or surgical nephrectomy, cyclosporine, or tacrolimus nephrotoxicity. 6. Metastatic malignancy which is actively being treated or may be treated by chemotherapy or radiation during the subsequent three month period after study therapy. 7. Chronic immunosuppression with the exception of corticosteroids up to a dose of 10 mg per day. 8. Known positive HIV or AIDS or COVID-19 9. Current Do Not Attempt Resuscitation (DNAR), Allow Natural Death (AND), or withdrawal of care status, or anticipated change in status within the next 7 days. 10. Patient not expected to survive 28 days because of an irreversible medical condition. (This is not restrictive to AKI, and may include situations such as the presence of irreversible brain damage, untreatable malignancy, inoperable life threatening condition, or any condition to which therapy is regarded as futile by the PI.) 11. Any medical condition that the Investigator thinks may interfere with the study objectives. 12. Treating clinician does not feel it is in the best interest of the patient 13. Platelet count <15,000/mm³ at time of screening. 14. Concurrent enrollment in another interventional clinical trial. Patients enrolled in clinical trials where only measurements and/or samples are taken (NO TEST DEVICE OR TEST DRUG USED) are allowed to participate. 15. Use of any other investigational drug or device within the previous 30 days. 16. Use of an AN-69 hemofilter membranes
Evaluation Plan	The primary evaluation of this study will be safety and all-cause mortality or dialysis dependency through 60 days post-enrollment. Additional endpoints will be time on CRRT, total ICU and hospital days. Mortality and dialysis dependency rates will be compared to historical controls.

LIST OF ABBREVIATIONS

ACD-A	Anticoagulant Citrate Dextrose- Formula A
AE	Adverse Event
AKI	Acute Kidney Injury
AIDS	Acquired Immunodeficiency Syndrome
AND	Allow Natural Death
ARDS	Acute Respiratory Distress Syndrome
ARF	Acute Renal Failure

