3. STUDY OBJECTIVES AND ENDPOINTS

3.1 PRIMARY OBJECTIVE

To evaluate the safety of up to ten consecutive 24 hour SCD treatments compared to historic data on in-hospital mortality and on all-cause mortality and dialysis dependency at day 28, and day 60 in the pediatric AKI population being treated with Continuous Renal Replacement Therapy (CVVH, CVVHD, or CVVHDF) with regional citrate anticoagulation.

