3.2 STUDY ENDPOINT

In this Pilot study four (4) domains of interest have been designated. The four (4) domains are:

1. Patient Safety: Safety Endpoint Measures include adverse events, laboratory safety parameters, vital signs, EKG, ventilation status and hemodynamic variables.
2. Clinical Efficacy: The Primary Clinical Efficacy Endpoint Measure is in-hospital; 28 and 60-day all-cause mortality. Time to renal recovery and necessity for chronic dialysis up to day 60 will also be determined. Additional efficacy endpoints include time to intensive care unit (ICU) discharge, and time to hospital discharge.
3. Device Integrity and Performance: The Endpoint Measure is SCD use without failure. This measure will help assess the integrity and performance of the SCD device.
4. SCD Mode of Action: Exploratory Endpoint Measures will include inflammatory cytokines, cell activation parameters and biomarkers at clinical sites with this capability.

Endpoints are defined as:

ALL-CAUSE MORTALITY:

All-cause mortality is defined as in-hospital, 28-day and 60-day all-cause mortality.

DIALYSIS DEPENDANCY AT DAY 60:

Dialysis dependency at day 60 is defined as patient not receiving any form of intermittent or continuous renal replacement therapy at or within 3 days of 60 days post enrollment in the study with no plans for additional intermittent or continuous renal replacement therapy.

PATIENT SAFETY:

Adverse events, laboratory safety parameters, vital signs, EKG, ventilation status and hemodynamic variables.

DURATION OF RENAL SUPPORT:

The duration of renal support will be defined as the numbers of days from the initiation of renal replacement therapy (start of observation period) to final dialysis treatment. Duration of renal support will be censored if the patient is still dialysis dependent at the time of death or are dependent at day 60.

RECOVERY OF RENAL FUNCTION:

Recovery of renal function will be defined as lack of need for continuous dialysis support on day 28, and will be classified as yes or no at day 28.

Subjects who were alive at day 28 will be included in the analysis.

Patients who remain dialysis dependent at study completion (day 60) or time of death will be categorized as having no recovery of renal function.

ASSESSMENT OF DEVICE INTEGRITY AND PERFORMANCE

Criteria for assessment of device integrity and performance include:

- Significant Clotting within the Device as assessed by visual inspection

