Besides the test of the hypothesis the study is focused on observable, empirical and laboratory determinations of subject safety while on the SCD. Previous human trials have been conducted on the SCD device and the protocol contains a review of AE and SAE data from all SCD human studies and findings from those studies contributed to constructing the investigative safety profile. Safety endpoint measures specified in the protocol include adverse events, laboratory safety parameters, vital signs, ventilation status and hemodynamic variables. Device integrity and performance measurements are also defined as are circumstances which demand premature termination of SCD treatment.

Prolonged exposure to the SCD is anticipated to result in superior outcomes, although as noted above, this pilot study is not designed to assess for efficacy. However, we understand that a minimum amount of exposure to the SCD will be required for an appropriate safety analysis and for making any inference regarding efficacy. The ppCRRT experience demonstrated that the majority of patients (201/370) received CRRT for 1 to 7 days and exhibited 65% survival (Symons et al CJASN 2007 Table7).

This trial is an early safety efficacy study but is not powered for statistical significance. Insights into a comparison of historical controls matched to SCD treated subjects will utilize the ppCRRT Registry to match for: etiology of AKI, co-morbidities, CRRT modality, dose and form of anticoagulant, adverse events. [10]

The ppCRRT Registry has data fields for the primary reason for CRRT, including AKI and its cause, as well as co-morbidities which will be matched for primary organ system involvement. The CRRT modality was evenly distributed between convective and diffusive modality, with 60% of the convective modalities provided as CVVH and 40% as CVVHDF. The anticoagulant protocol will be standardized with ACD-A/CaCl₂ and all centers used the same protocol in ppCRRT Registry as outlined in this study protocol. Thus, the ppCRRT Registry dataset will be able to be matched to our study subject cohort. Also as noted above, subjects will be matched for age, size and PRISM II score.

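### The statements labelled primary disagree on the lead efficacy outcome: mortality at three unranked time points, mortality plus dialysis dependency, or death or dialysis through Day 60

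*Combined protocol and SAP*

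**What the plan says.** Several statements in the protocol carry the label primary.

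- **Synopsis, Primary Objective:** "To evaluate the safety of up to ten consecutive 24 hour SCD treatments in the pediatric AKI population being treated" with CRRT and regional citrate. No mortality, dialysis or comparator element appears.
- **Section 3.1, Primary Objective:** the same safety aim, now "compared to historic data on in-hospital mortality and on all-cause mortality and dialysis dependency at day 28, and day 60".
- **Section 3.2 and synopsis, Study Endpoints (same sentence in both):** "The Primary Clinical Efficacy Endpoint Measure is in-hospital; 28 and 60-day all-cause mortality". Renal recovery and the need for chronic dialysis are listed after it as further determinations.
- **Synopsis, Evaluation Plan:** "The primary evaluation of this study will be safety and all-cause mortality or dialysis dependency through 60 days post-enrollment". Its closing sentence sets rates of mortality and of dialysis dependency, in the plural, against historical controls.

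The synopsis Rationale gives the primary hypothesis as "up to ten sequential 24-hour SCD treatments will improve survival in pediatric patients with Acute Kidney Injury (AKI) as compared to CRRT alone", with no time point. Section 12 restates it against historical data, and also says that "this pilot study is not designed to assess for efficacy". On size, the synopsis says "Up to 10 patients will be enrolled in this study". Sections 3.2 and 12 say that the trial is not powered for significance. Section 12 offers basic statistics, historical comparison and subset analysis where suitable, and expects the results to inform a later pivotal design.

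**The concern.** These statements do not name the same lead efficacy outcome. They differ on whether dialysis belongs in it, on which time point leads and, in the Evaluation Plan, on whether death and dialysis form one outcome or two. Nothing in the available text ranks them or sets a success criterion.

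The study is open-label and small, and its efficacy reading rests on a comparison with registry controls. If the lead measure is not fixed in advance, whichever of the named measures compares best could be reported as the primary finding and carried into the pivotal design.

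The sponsor's earlier randomised trial, as reported in section 2.5, shows that the two kinds of measure can give different messages. In the recommended-calcium subgroup the 60-day mortality result is called borderline. Death or dialysis dependency in Table 9 is 3/19 (15.8%) against 15/27 (55.6%), p = 0.007.

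**Working it through.** The plan has no sample-size, alpha or power figure to reproduce. The check sets the statements against the same children and then asks how often they would diverge.

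**Step 1. Four hypothetical children under each measure.** Dialysis dependency is taken in its ordinary sense.

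| Child | In-hospital death | Day 28 death | Day 60 death | Dialysis, Day 28 / Day 60 (3.1) | Day 60 death or dialysis, if composite |
|---|---|---|---|---|---|
| A: alive at Day 60, on dialysis throughout | no | no | no | yes / yes | yes |
| B: off dialysis, discharged, dies Day 45 | no | no | yes | no / no | yes |
| C: off dialysis by Day 28, dies in hospital Day 40 | yes | no | yes | no / no | yes |
| D: on dialysis at Day 28, off before Day 60, alive | no | no | no | yes / no | no |

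Child A is a success on all three mortality measures in 3.2, but has the adverse outcome on dialysis in 3.1 and on a composite reading of the Evaluation Plan. Child B separates in-hospital from 60-day mortality, which share one sentence in 3.2. Child D matters only under 3.1, unless the Evaluation Plan's wording is taken to cover dialysis at any time up to Day 60. These are different outcomes, not variants of style.

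**Step 2. How likely is a child like A?** Inputs:
- Mortality of 35%, being 1 minus the 65% survival that section 12 cites for registry patients on CRRT for 1 to 7 days, or about 50% (synopsis Rationale).
- Renal non-recovery of 10–20% (synopsis Rationale), assumed here to apply to survivors.
- n = 10.

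Probability per child = (1 − mortality) × non-recovery. Chance of at least one = 1 − (1 − that probability)^10.

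- Lowest: 0.50 × 0.10 = 0.05; 1 − 0.95^10 = 0.40.
- Highest: 0.65 × 0.20 = 0.13; 1 − 0.87^10 = 0.75.

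The mortality-only and death-or-dialysis statements would thus probably classify at least one child differently over most of this range.

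**Step 3. Precision of whichever measure leads.** For 3 events in 10, the exact (Clopper–Pearson) 95% interval runs from 6.7% to 65.2%. It contains both 35% and 50%. A contrast between one measure and another in this trial would therefore carry little information, which is why the lead measure should be settled on paper beforehand.

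**The case against.** The protocol separates four domains, so a safety objective can coexist with a labelled efficacy measure, and section 3.1 can be read as an expansion of the synopsis objective. A reader might infer four mutually exclusive primaries; the text does not support that. The synopsis and section 3.2 also agree word for word on the efficacy measure. This part stands. The disagreement is confined to sections 3.1 and 3.2 (with its synopsis twin) and the Evaluation Plan.

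The Evaluation Plan need not be a composite: its plural rates fit two separate outcomes, close to section 3.1. This also stands, and it means the sentence must be clarified, not that it is clear. If it is a composite, 60-day mortality is only a component of it and is not common to every efficacy statement.

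A reader might also want to attach a false-positive figure to the conflict. The plan gives no test, alpha or success rule to inflate, and the candidate measures overlap. For example, assume 35% mortality and 15% of survivors on dialysis. The composite rate is then 0.35 + 0.65 × 0.15 = 44.75%. Looking at least 15 points better on the composite needs 2 or fewer events in 10. That already means 2 or fewer deaths, which meets the same margin on 60-day mortality (35% − 15% = 20%). In that setting the composite adds no extra chance of a favourable result; any gain comes from the three mortality time points within 3.2.

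Nor is it a bias that each dialysis-dependent survivor raises the composite above mortality, because the controls' composite rises too.

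Finally, all these outcomes are named in advance, and nothing suggests that selection is intended.

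**Conclusion.** The contradiction is real and nothing in the available text resolves it. The lead efficacy outcome is mortality at three unranked times in 3.2, has dialysis dependency beside it in 3.1, and is death or dialysis of unclear construction in the Evaluation Plan.

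Its weight is moderate. In an unpowered descriptive study of up to 10 children, it leaves room for selective emphasis in a historical comparison that is meant to guide a pivotal trial. It does not breach a stated error rate and is not evidence of intent. The 40–75% in step 2 rests on applying the protocol's general mortality and non-recovery figures to this cohort, with children independent. It measures how often the definitions would diverge, not a bias. The point should be corrected before data are reviewed.

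**What to change.** Use one identical statement in the synopsis, section 3.1, section 3.2 and the Evaluation Plan.

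- **Primary objective:** safety, reported descriptively.
- **Lead efficacy measure:** one measure at one time point, named before data are reviewed. All-cause mortality at 60 days is the natural default: it lies within the measure already labelled primary in both synopsis and body, and it matches the survival hypothesis. The sponsor may instead justify the Day 60 death-or-dialysis composite; section 2.5.4 shows an intention to use such a composite in a new trial after the earlier one.
- **Evaluation Plan:** state whether death and dialysis dependency form a composite or are two separate outcomes.
- **Secondary:** in-hospital and 28-day mortality, and the remaining dialysis or composite measure. Report every measure with an exact 95% confidence interval, whatever the result.

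Any measure that uses dialysis also needs its definition in 3.2 corrected. As written, it describes a patient who is not receiving renal replacement, and it covers Day 60 only, although 3.1 uses Day 28 as well.

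The cost is wording only. Enrolment, procedures and data collection do not change. The sponsor gives up the freedom to choose the leading result afterwards.

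### Censoring duration of renal support at death on dialysis overstates the chance of coming off RRT, and CRRT, ICU and hospital days carry no death rule

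*Combined protocol and SAP*

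**What the plan says.** Section 3.2 defines duration of renal support as the "numbers of days from the initiation of renal replacement therapy (start of observation period) to final dialysis treatment". Its rule for incomplete observations is: "Duration of renal support will be censored if the patient is still dialysis dependent at the time of death", and the same sentence applies censoring to dependence at day 60. Death on dialysis and dependence at day 60 are therefore handled alike.

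The next endpoint in Section 3.2, recovery of renal function, treats the same child differently: "Patients who remain dialysis dependent at study completion (day 60) or time of death will be categorized as having no recovery of renal function". It also restricts its analysis set: "Subjects who were alive at day 28 will be included in the analysis".

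Other duration measures are named without any rule for death in the text available:

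- Section 3.2: "Time to renal recovery and necessity for chronic dialysis up to day 60 will also be determined".
- Synopsis (Study Endpoints) and Section 3.2: "Additional efficacy endpoints include time to intensive care unit (ICU) discharge, and time to hospital discharge".
- Synopsis (Evaluation Plan): "Additional endpoints will be time on CRRT, total ICU and hospital days".

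No estimator is given for any of these. Section 12 promises only basic statistics with historical comparisons.

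**The concern.** A child still dependent at day 60 is an unfinished observation, because dialysis may yet stop. A child who has died on dialysis is not, because that child cannot come off. Standard censoring gives both the same meaning: they would later have come off at the rate seen in those still at risk. At the mortality the protocol cites, this is a large imputation. It also leaves one child a known failure on the recovery endpoint and an open outcome on the duration endpoint.

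The measures with no death rule raise a second, separate problem. If CRRT, ICU or hospital days are summarised as raw days, a child who dies on day 3 contributes 3 days, among the most favourable values on the scale.

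The rationale (Section 1.1) hypothesises that the device shortens dialysis, and Section 12 says the results will help design a pivotal study. A duration summary that cannot tell recovery from death is a poor basis for that.

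**Working it through.** The plan states no expected duration or recovery rate, so there is no figure to reproduce. The following is an illustration.

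**Inputs**

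- Mortality 50%: the approximate rate for critically ill patients with AKI in the Synopsis rationale.
- Mortality 35%: from 65% survival in Section 12. That figure is for registry patients on CRRT for 1 to 7 days, not the whole registry.
- Dependency 10-20%: the share of AKI patients said not to recover (Section 1.1). Applying it to day-60 survivors is my assumption.
- Constant hazards, one common day 0 and a 60-day horizon are also my assumptions.

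**Formulas.** Let D be the probability of death on RRT by day 60, R the probability of coming off RRT, and q = 1 - D - R the probability of still being on RRT. The total hazard is L = -ln(q)/60, and the recovery hazard is r = L x R/(R + D). The true probability of coming off is R. The censored estimate is 1 - exp(-60r) = 1 - q^(R/(R + D)).

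**All deaths on RRT**, so R = (1 - D) x (1 - dependency):

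| D | Dependency | R (true) | q | Censored estimate |
|---|---|---|---|---|
| 0.50 | 10% | 0.450 | 0.050 | 1 - 0.050^(0.450/0.950) = 0.758 |
| 0.50 | 20% | 0.400 | 0.100 | 1 - 0.100^(0.400/0.900) = 0.641 |
| 0.35 | 10% | 0.585 | 0.065 | 1 - 0.065^(0.585/0.935) = 0.819 |
| 0.35 | 20% | 0.520 | 0.130 | 1 - 0.130^(0.520/0.870) = 0.705 |

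**Only half of deaths on RRT**, with the other half coming off RRT first. D is 0.25 or 0.175 and R = 1 - D - q, with q as in the table. The true values are 0.65-0.76 and the censored estimates 0.80-0.89. The bias remains but is smaller.

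**Response to deaths.** Take 50% mortality and 15% dependency. Then R = 0.425, q = 0.075, L = 0.0432, r = 0.0198 and the death hazard is 0.0233 per day. Double the death hazard alone, so the total is 0.0665:

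- Mean raw RRT days, (1 - exp(-60 x total))/total, fall from 21.4 to 14.8, an apparent improvement.
- The censored estimate, 1 - exp(-60r), stays at 70%, because the death hazard is not in it.
- The true probability of coming off falls from 43% to 29%.

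**Invented ten-child example.** Deaths on RRT at days 2, 3, 4, 5 and 6; children off RRT at days 8, 10, 14 and 21; one dependent at day 60.

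- Censored curve: five children are at risk from day 8, so the curve steps 0.8, 0.6, 0.4, 0.2. It shows 80% off RRT with a median of 14 days.
- Truth: 4/10 = 40% come off, so the median is never reached.
- Raw days: median (6 + 8)/2 = 7.0, mean 133/10 = 13.3. The five deaths are the five shortest values.
- RRT-free days to day 60 with zero for death: 52, 50, 46, 39 and six zeros, mean 187/10 = 18.7.

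**The case against.** Several counter-arguments have force.

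- **No estimator is named.** Censoring at death is legitimate for a cause-specific hazard; the error lies in reading one minus Kaplan-Meier as a probability. This stands. The bias follows from the usual use of a censored duration, not from a stated analysis, which is a reason to name the estimator.
- **Early death does not improve the censored estimate.** A reader might infer that every one of these endpoints looks better when children die early. The documents do not support that. A death censored on day 3 means at least 3 days, and doubling the death hazard left the estimate unchanged. Only raw-day summaries improve. Time to ICU or hospital discharge is a time-to-event measure, and a child who dies before discharge never has the event; what is missing there is the competing-event rule.
- **The endpoint called recovery is not inflated by this rule.** It classes dependence at death as no recovery. Its restriction to children alive at day 28 can raise the rate (4/5 against 4/10 in the example), but that is a different provision.
- **More dramatic figures are available.** Hazards of 0.05 per day each for recovery and death give 95.0% shown against 49.9% true. But they leave only 0.5% of survivors dependent at day 60 (0.0025/0.501), far below the protocol's 10-20%, and they put every death on RRT. I do not rely on them.
- **Impact is limited.** Section 3.2 says the trial is unpowered and the Synopsis caps it at 10. Death counts in the primary evaluation, and the Evaluation Plan names only mortality and dialysis dependency for historical comparison. This bounds the importance but does not make the rule right.
- **Free days with zero for death largely restate mortality when half the children die.** Fair, and a reason to show cumulative incidence and individual outcomes alongside.

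**Conclusion.** The point holds for two distinct mechanisms. First, the rule in Section 3.2 makes any standard censored summary of renal support overstate the probability of coming off RRT and ignore deaths. If all deaths occur on RRT, the overstatement is about 24 to 31 percentage points at 50% mortality and 19 to 23 at 35%; with half of deaths on RRT, about 11 to 19. These sizes rest on constant hazards and on applying the protocol's 10-20% non-recovery to survivors. Second, CRRT, ICU and hospital days have no death rule in the text available, so raw-day summaries would count early deaths as favourable.

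Mortality, death-or-dialysis and the binary recovery endpoint are not affected by the censoring rule. The change should be made, but it concerns additional endpoints in a small pilot and does not threaten the primary evaluation.

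**What to change.** In Section 3.2, replace censoring at death with one or both of:

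- cumulative incidence of coming off RRT, with death as a competing event and censoring only at day 60 or loss to follow-up;
- RRT-free days to day 60, with zero for any child who dies by day 60.

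For analysis, count RRT stopped at withdrawal of life support as death on RRT. Section 7.2 item 5 lists withdrawal as a reason to end device treatment but does not say how the end of RRT is then classified.

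Apply the same death rule to time to renal recovery, time on CRRT, and ICU and hospital stay. List each child's outcome and dates, and give raw days among survivors as description only.

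**Cost.** RRT dates are collected at days 28 and 60 (Sections 6.6.2 and 6.6.3), and deaths are captured as serious adverse events to day 60 (Sections 9.2 and 9.7.2), so the RRT change is wording. ICU and hospital stay need more: discharge dates are listed at the day-28 contact but not at day 60. Either use a day-28 horizon for those two measures or add two date fields to the day-60 contact. The other cost is that reported recovery will look less favourable.

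### Dialysis dependency at day 60 is defined as its opposite, day-28 dependency is not defined, and the day-28 recovery rule names only continuous dialysis

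*Combined protocol and SAP*

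**What the plan says.** Section 3.2 gives the day-60 definition: "Dialysis dependency at day 60 is defined as patient not receiving any form of intermittent or continuous renal replacement therapy at or within 3 days". The window is set around day 60 counted from enrollment, and a further condition is added: "with no plans for additional intermittent or continuous renal replacement therapy".

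Recovery is defined in the same section by three sentences:

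1. "Recovery of renal function will be defined as lack of need for continuous dialysis support on day 28", classed yes or no at that day.
2. "Subjects who were alive at day 28 will be included in the analysis".
3. "Patients who remain dialysis dependent at study completion (day 60) or time of death will be categorized as having no recovery of renal function".

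These measures are used elsewhere. The primary objective (section 3.1) makes a comparison with historic data on "all-cause mortality and dialysis dependency at day 28, and day 60". The synopsis, under Evaluation Plan, says: "Mortality and dialysis dependency rates will be compared to historical controls". Section 11 has the DSMB assess dialysis dependency alongside mortality.

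Three operational sections matter too. Section 7.2, item 1, foresees that a child may improve enough to move from CRRT to intermittent hemodialysis (IHD). Sections 6.6.2 and 6.6.3 count day 28 and day 60 from enrollment and record the presence and dates of RRT since the last visit. Footnote 3 of the schedule in section 6.3 counts the follow-up visits from SCD initiation.

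**The concern.** A measure that is to be set against historical controls needs a definition that can be applied as written, and the same way in both groups. Here the day-60 definition points the wrong way and the day-28 one is missing. The recovery rule is the nearest day-28 renal definition, but it uses a word, *continuous*, that may mean either the modality (CRRT as opposed to IHD) or simply ongoing dialysis. The dependency definition in the same section sets intermittent and continuous therapy side by side as modalities, so the literal reading is a reasonable one.

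With at most ten children in an open-label study, classing a single child differently moves a proportion by ten points or more. If the reading is settled only after the results are known, the choice can follow the result.

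**Working it through.** The plan states no figure for these measures, so there is none to reproduce. The check sets the sentences against each other and then sizes the one conflict that they cannot resolve.

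**Dependency at day 60.** The text requires two things together: no RRT in the window, and no RRT planned. The logical opposite is: RRT in the window, *or* RRT planned. Merely striking the word *not* does not repair it, because the text would then describe a child on RRT with none planned. The plan's own history shows how far off the literal wording is. In ARF-002 (section 2.4.1; adults, day 60) mortality was 31.4% of 35, and 0.314 × 35 = 10.99, so 11 died and 35 − 11 = 24 survived, all dialysis independent. If none of them had further RRT planned, the literal wording would class 24/24 as dependent instead of 0/24.

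**Recovery at day 28.** Possible courses under the three sentences:

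| Course | Sentence 1, *continuous* = modality | Sentence 1, *continuous* = ongoing | Sentence 2 | Sentence 3 |
|---|---|---|---|---|
| Dies on RRT before day 28 | – | – | excluded | no recovery, if it reaches early deaths |
| IHD at day 28, then dependent at day 60 or at a death in between | yes | no | included | no recovery |
| IHD at day 28, off by day 60 | yes | no | included | silent |
| Off at day 28, dependent at day 60 or at a later death | yes | yes | included | no recovery only if *remain* covers a restart |
| CRRT at day 28, off by day 60 | no | no | included | silent |
| Off at both days | yes | yes | included | silent |

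The second row is settled if sentence 3 overrides sentence 1. The third row is settled by nothing in the text. The first and fourth rows depend on an order, and on a meaning of *remain*, that the plan does not state.

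**Size.** Assume six survivors of day 28, five off all RRT and one on IHD.

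- IHD child still dependent at day 60: sentence 1 alone gives 6/6; all three sentences give 5/6.
- IHD child off by day 60: 6/6 = 100% (exact 95% CI 54.1 to 100) under the modality reading, 5/6 = 83.3% (35.9 to 99.6) under the ongoing reading. Difference: 100/6 = 16.7 points.

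The number of survivors is an assumption. The plan quotes mortality of about 50% (synopsis) and 65% survival among registry patients with 1 to 7 days of CRRT (section 12). Applied to ten children, these give 3.5 to 5 deaths, hence about five to seven survivors if all those deaths fall before day 28. One child then counts for 100/5 = 20.0, 100/6 = 16.7 or 100/7 = 14.3 points. With no such child the difference is zero.

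**Anchor.** Section 6.4 has the baseline period run from enrollment to the start of SCD treatment, so the two starting points are distinct. The plan gives no fixed interval between them.

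**The case against.** The strongest reply is that the three recovery sentences can be read together: sentence 2 sets who is analysed, and sentence 3 then applies to those who survived day 28. That is the most natural joint reading and it uses every sentence. It gives a single answer, 5/6, when the IHD child stays dependent to day 60. This stands, but the text does not state that order, and the reading leaves the child on IHD at day 28 who is off by day 60 unclassified.

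Three stronger inferences are tempting and should not be drawn.

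- A reader might put 6/6 beside 5/10 (the same children with four early deaths added) and infer a 50-point ambiguity. The documents do not support that: 6/6 ignores sentence 3 for a child who stays dependent, and 5/10 ignores sentence 2.
- A reader might infer that every child who restarts dialysis after day 28 is classed in two ways. Sentence 3 speaks of patients who *remain* dependent, which may not cover a restart.
- A reader might infer that contacts up to seven days after day 60 cannot establish status within three days of it. Because RRT dates since the last visit are recorded, a later contact can still fix the status, so no loss of data is shown.

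The stakes are also limited. Mortality is the primary efficacy measure, the pilot is not powered, and no section says that the day-28 recovery class itself will be compared with controls. That the recovery rule might stand in for day-28 dependency is an inference; the day-60 definition could equally be carried back. These limits bear on the recovery rule. They do not excuse the inverted dependency definition, since dependency rates are explicitly to be compared.

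**Conclusion.** The point holds. Two faults are plain on the page: day-60 dependency is defined as independence, and day-28 dependency, named in the primary objective, has no definition. A third is a literal reading that the text allows and does not correct: a child on IHD at day 28 who is off by day 60 counts as recovered. That is worth 16.7 points per child among six assumed survivors (14.3 to 20.0 with seven to five). Two lesser gaps are the unstated order of sentences 2 and 3 and the two starting points for the day count.

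The size rests on assumed counts, not on trial estimates. Mortality results are untouched, and the documents do not show which way any bias against the controls would run. The definitions should be corrected before the data are analysed.

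**What to change.** 1. Define dialysis dependency as receiving, or planned to receive, any intermittent or continuous RRT. Apply it at day 28 and at day 60, with one anchor for both days, and derive status from the recorded RRT dates.
2. Define recovery at day 28 as free of any intermittent or continuous RRT.
3. State the order of the three recovery sentences, including how deaths before day 28 are handled, and say whether dependency at day 60 in a child who was off RRT at day 28 changes the day-28 class.
4. Keep the survivor denominator that the plan states. Beside it, report the number alive and free of any RRT among all treated children, with deaths and unknown status as separate counts. In the example above, if the six survivors came from ten treated children with four early deaths, this would read 5/6 and 5/10. ARF-002 shows why both are useful: 24/24 of survivors, but 24/35 = 68.6% of all subjects (adults at day 60, so an indication of scale only).

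The cost is revised wording and one extra line of analysis. The treated children need no new field, because RRT presence and dates are already recorded at both contacts. Whether the historical registry holds RRT status at day 28 and day 60 is not shown and has to be checked before the same definition can be applied to controls. The downside is a possibly lower reported recovery rate.
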